**For subjects randomized under protocol version 6.0, or 7.0 or 8.0:**

Study drug can be reduced by 20% of the current dose at which the AE leading to temporary stop occurred, once platelets and/or white blood cell and/or hemoglobin are normalized, and/or triglycerides return to levels below 300 mg/dL (3.42 mmol/L), or diarrhoea is mild. The subject may have more than the usual number of scheduled visits if needed, until the AE resolves, and then will continue the study as per scheduled visits.

In addition, in case a subject will have a consistent (e.g., at least two consecutive evaluation) platelets count  $\leq 150 \times 10^9/L$  and not meeting the stopping criteria for platelets, the Investigator will have to reduce the dose by 20% of the current dose (see Section 8.2.2 for more details).

For subjects randomized under protocol version 6.0 or 7.0 or 8.0, only one dose reduction is allowed during the treatment period.

Any decision relevant to the dose interruption and/or modification of the schedule of assessments can be discussed with the Medical Monitor, but the final decision remains with the Investigator only or its authorized designee.

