
Dose adjustment:
	
In case the study drug is temporarily stopped, the study drug can be resumed at a level 20% smaller (see table below) than the one at which the AE leading to temporary stop occurred, once platelets and/or white blood cell and/or hemoglobin are normalized and/or triglycerides return to levels below 300 mg/dL (3.42 mmol/L ) or diarrhoea is mild.
 
  
 Rules for Dose Reduction of 20%	
 
 Starting Dose (mg) bid	13.3	16.7	20	23.3	26.7	33.3	36.7	40	46.7	
   
 Oral suspension (mL) bid	1.3	1.7	2.0	2.3	2.7	3.3	3.7	4	4.7	
  
	Rules for Dose Reduction of 20%										Starting Dose (mg) bid	13.3	16.7	20	23.3	26.7	33.3	36.7	40	46.7	Oral suspension (mL) bid	1.3	1.7	2.0	2.3	2.7	3.3	3.7	4	4.7
Rules for Dose Reduction of 20%																															
Starting Dose (mg) bid	13.3	16.7	20	23.3	26.7	33.3	36.7	40	46.7																						
Oral suspension (mL) bid	1.3	1.7	2.0	2.3	2.7	3.3	3.7	4	4.7																						

Reduced Dose (mg) bid	10.6	13.4	16	18.6	21.4	26.6	29.4	32	37.4
Oral suspension (mL) bid	1.1	1.3	1.6	1.9	2.1	2.7	2.9	3.2	3.7

In addition, in case a subject will have a consistent (e.g., at least 2 consecutive evaluations) platelets count  $\leq 150 \times 10^9/L$  and not meeting the stopping criteria for platelets, the Investigator will have to reduce the dose by 20% of the current dose.

Only one dose reduction is allowed during the treatment period.

**Subjects who were randomized under protocol version 4.0**, will continue to follow the instructions of protocol version 4.0, related to starting dose and dose modifications:

In case the study drug was temporarily stopped, the study drug can be resumed at a level 1/3 smaller (see table below) than the one at which the AE leading to temporary stop occurred, once platelets and/or white blood cell and/or hemoglobin are normalized and/or triglycerides return to levels below 300 mg/dL (3.42 mmol/L) or diarrhoea is mild.

Rules for Dose Reduction of 1/3									
Starting Dose (mg) bid	20	25	30	35	40	50	55	60	70

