#### ***4.2.2 Clinical Experience with Givinostat Including Risks and Benefits***

Completed and updated data that describe the clinical experience with givinostat are reported in Section 6 “Effects in Humans” of the current Investigator Brochure Dossier related to ITF2357.

Givinostat has been tested in a number of clinical studies in adults and paediatric populations. Three major indications have been explored with Givinostat, chronic inflammatory diseases, neuromuscular disorder and oncology. The maximum administered dose was a single dose of 600 mg in healthy volunteers and up to 400 mg once per week in subjects with multiple myeloma. Doses up to approximately 100 mg bid were generally well tolerated in adults. In paediatric subjects, doses up to 0.75 mg/kg bid have been administered for up to 6 months (with 1 additional subject having been treated for 2 years and 7 months) in patients with Juvenile Idiopathic Arthritis. In subjects with DMD enrolled in study DSC/11/2357/43 (i.e., subjects between 7 and 10 years of age at study start), the maximum dose administered in the dose escalation phase was 50 mg bid for up to 2 weeks i.e., while the maximum dose administered for up to 1 year in the second part of the study was 37.5 mg bid. Since, clearance increases with increased weight (see Section 8.2.1) doses have been increased in the extension phase of study DSC/11/2357/43 due to the increase in weight of the enrolled children; as a result the maximum dose administered in this extension phase is 60 mg bid.

The most common AEs observed were thrombocytopenia, as well as gastrointestinal toxicities. Adverse events were generally mild to moderate and reversible upon discontinuation of study drug. Moreover, dose-dependent asymptomatic and reversible platelets count reductions were observed both in healthy volunteers and subjects treated with givinostat. These decreases typically occurred within the first week after treatment initiation, reached a nadir after 2 to 3 weeks of treatment, and then remained at a plateau (see the IB, Section 7). The majority of thrombocytopenic events were mild in severity with fewer than 10% of subjects developing platelets count below  $75 \times 10^9/L$ . All occurrences resolved completely within 2 to 3 weeks of discontinuation of treatment, suggesting a rapidly reversible effect. Overall, sixteen haemorrhagic drug-related AEs were reported by 14 patients

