**Table 4: Placebo or Givinostat Dose Modification for subjects randomized under study protocol version 6.0 or 7.0 or 8.0.**

Weight (kg)	$\geq 10$ and $< 12.5$	$\geq 12.5$ and $< 20$	$\geq 20$ and $< 25$	$\geq 25$ and $< 30$	$\geq 30$ and $< 40$	$\geq 40$ and $< 50$	$\geq 50$ and $< 60$	$\geq 60$ and $< 70$	$\geq 70$
Starting Dose (mg) bid	13.3	16.7	20	23.3	26.7	33.3	36.7	40	46.7
Oral suspension (mL) bid	1.3	1.7	2.0	2.3	2.7	3.3	3.7	4	4.7
Reduced Dose (mg) bid	10.6	13.4	16	18.6	21.4	26.6	29.4	32	37.4
Oral suspension (mL) bid	1.1	1.3	1.6	1.9	2.1	2.7	2.9	3.2	3.7

Study drug can be resumed at a level 20% smaller than the dose at which the AE leading to temporary stop occurred, once platelets and/or white blood cell and/or hemoglobin are normalized and/or triglycerides return to levels below 300 mg/dL (3.42 mmol/L) or when diarrhoea is mild.

For subjects randomized under protocol version 6.0 or 7.0 or 8.0, only one dose reduction is allowed during the treatment period.

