**Dose Modification (all subjects):**

If subjects (i.e. those already in treatment or those who will be randomized under protocol version 6.0 or 7.0 or 8.0) gain weight during the study the drug dose must be kept unchanged.

If subjects (i.e. those already in treatment or those who will be randomized under protocol version 6.0 or 7.0 or 8.0) lose weight during the study, the drug dose should be adjusted

according to Table 2 or Table 3 if the subject is still on treatment at starting dose, or according to Table 4 or Table 5 if the subject has already reduced the starting dose.

All subjects will be asked to have platelets count assessments weekly during the first month of treatment and performed every two weeks during the second month of treatment, in order to strictly monitor this parameter for safety reasons.

If the dose is reduced due to platelet count  $\leq 150 \times 10^9/L$ , and/or white blood cell  $< 3.0 \times 10^9/L$  and/or hemoglobin  $< 10.0 \text{ mg/dL}$  a complete blood count (i.e.CBC) test must be performed weekly for 8 consecutive weeks.

If a dose adjustment and/or modification of schedule of assessments is decided by the Investigator or authorized designee, it is advised to discuss this decision with the Medical Monitor, however this is not mandatory as the Investigator is the only responsible for the medical care of the subject and the Investigator's decision should not be influenced, deleted nor approved by the Medical Monitor.

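### For boys on protocol versions 6.0–8.0 who have already been reduced once, the mandatory 20% platelet reduction and the one-reduction limit cannot both be followed, and the dose on resuming after a further temporary stop is not stated

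*Protocol*

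**What the plan says.** Three places in the protocol set the dose-modification rules for boys randomised under versions 6.0–8.0: the Synopsis (Dose adjustment), Section 7.3.1, and Section 8.2.2 with Table 4. Each contains the same three elements.

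- **Platelet rule.** With consistent counts (at least two in a row is the example given) at or below 150 x 10^9/L "and not meeting the stopping criteria for platelets", the instruction is that "the Investigator will have to reduce the dose by 20% of the current dose".
- **Resumption rule.** After a temporary stop for platelets, white cells, haemoglobin, triglycerides or diarrhoea, and once the trigger has settled, Section 8.2.2 says: "Study drug can be resumed at a level 20% smaller than the dose at which the AE leading to temporary stop occurred".
- **Limit.** Section 7.3.1 states: "For subjects randomized under protocol version 6.0 or 7.0 or 8.0, only one dose reduction is allowed during the treatment period". The Synopsis has the same limit: "Only one dose reduction is allowed during the treatment period".

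Boys randomised under version 4.0 are treated differently. After their one-third reduction, a further 20% step is expressly allowed (Synopsis; Sections 7.3.1 and 8.2.2).

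**The concern.** The platelet rule is mandatory, is expressed relative to the current dose, and is not confined to boys still on their starting dose. The limit is absolute. Once a boy has used his one reduction, a later platelet trigger calls for a step that the limit forbids, and nothing says which rule gives way.

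Staying on the reduced dose, reducing again and stopping are three different treatments. The choice concerns platelet reduction, one of the drug's most common adverse effects, in children at about 50 sites. If sites settle it differently, the dose delivered after the first trigger depends partly on the site, and most plausibly in the givinostat arm, where platelet falls are expected. A boy taken off treatment would have an early withdrawal visit within two weeks (Protocol Section 9.1.8). His later scheduled 4SC values would then be imputed under SAP Section 4.4.4.1, by default with the mean for his treatment, steroid stratum and group.

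**Working it through.** No sample-size or power calculation bears on this. The check sets the rules against each situation a version 6.0–8.0 boy can be in, and then looks in the dose table for a second step.

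**1. Rules side by side** (platelets x 10^9/L)

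| Situation | Platelet or stopping rule | One-reduction limit | Result |
|---|---|---|---|
| Not yet reduced; consistent counts 75–150 | Reduce 20% | Allows it | One action |
| Already reduced for platelets; consistent counts 75–150 again | Reduce 20% of current dose | Forbids it | Conflict |
| Already reduced after a stop for, say, triglycerides or diarrhoea; consistent counts 75–150 for the first time | Reduce 20% of current dose | Forbids it | Conflict |
| Already reduced; meets a temporary-stop trigger | Stop; only resumption level described is 20% lower | Bars that level | Stop defined, resumption dose not stated |
| Confirmed count of 50 or below | Permanent stop | Not relevant | One action |

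The range 75–150 follows from Section 7.3.1: counts below 75 but above 50 call for a temporary stop, and counts of 50 or below, once confirmed, for a permanent one.

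**2. Table 4.** The plan's figures reproduce as a single step, starting dose x 0.8 rounded to 0.1 mg:

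- 13.3 → 10.6; 16.7 → 13.4; 20 → 16
- 23.3 → 18.6; 26.7 → 21.4; 33.3 → 26.6
- 36.7 → 29.4; 40 → 32; 46.7 → 37.4

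All nine agree with the table, and the volumes agree at 10 mg/mL. There is one reduced-dose row. Applying the platelet rule literally a second time would give 0.8 x 0.8 = 0.64 of the starting dose. No weight band has an entry for that. (This is arithmetic only, not a proposed dose.)

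**3. Comparison with version 4.0.** The version 4.0 starting dose x 2/3 equals the version 6.0–8.0 starting dose in all nine bands (for example 20 x 2/3 = 13.3 and 70 x 2/3 = 46.7). A version 4.0 boy who takes the extra 20% step therefore reaches the same dose as a version 6.0–8.0 boy after his single step.

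**4. Timing.** After a reduction for platelets at or below 150, Section 8.2.2 says a complete blood count "test must be performed weekly for 8 consecutive weeks". With the example of two consecutive counts, the trigger could recur about two weeks after the reduction. This shows that the protocol monitors for the situation. It does not show how often it occurs.

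**The case against.** The best reply is that the limit follows directly after the order in Section 7.3.1 and is naturally read as qualifying it: reduce once, then stay there. Both worked examples in Section 8.2.2 begin from the starting dose, Table 4 has one reduced row, and both protocol cohorts end at the same lowest dose. That is a coherent reading and may be what was intended. But it is not written anywhere, and it sets aside a mandatory instruction. Limiting the order to its first use also leaves out the boy whose one reduction followed a stop for triglycerides or diarrhoea and whose platelets then trigger the order for the first time.

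The reply also says that the Investigator has the final decision on dose adjustment (Synopsis; Section 8.2.2) and may end treatment at any time. That says who decides, not what the rule is. Section 8.3 refers to an operations manual for more detail. It is not available here, and it would not remove the conflict from the protocol.

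Several stronger readings are tempting, and the documents do not support them.

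- **That no compliant action exists.** The temporary and permanent stops apply whatever the earlier reductions, discretionary cessation is open, and the resumption wording is permissive. A temporary stop in a boy already reduced leaves a gap in the resumption dose, not a strict contradiction.
- **That sites will dose differently.** The text supports only that they may. The SAP Section 3.5 flag for more than one reduction is no evidence of divergence, because version 4.0 boys may properly have two.
- **That the conflict will be met often.** Section 8.2.1 reports that about 50–60% of blinded subjects with at least 8 weeks of treatment needed a platelet-driven reduction. Dividing by the two-thirds on givinostat gives 75–90% (0.50/0.667 and 0.60/0.667). But these are first reductions, at starting doses 1.5 times those at issue (20/13.3), and the division assumes none on placebo.
- **That platelets stay low after a reduction.** Section 4.2.2 says on-treatment counts "reached a nadir after 2 to 3 weeks of treatment, and then remained at a plateau". It also reports complete resolution within 2 to 3 weeks of stopping and calls the effect rapidly reversible. It does not describe counts after a 20% reduction.

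**Conclusion.** The point holds within stated bounds. For a version 6.0–8.0 boy who has already been reduced for any reason, two stated rules give opposite instructions when platelets are consistently 75–150 x 10^9/L. If he is temporarily stopped, his resumption dose is not stated. The pairing appears in three places and nothing in them resolves it.

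The number of boys affected cannot be estimated, because the documents give no rate of repeat or second-cause triggers at the version 6.0–8.0 doses. Differing practice between sites and lost 18-month 4SC data are possible consequences. They are not demonstrated: no rule directs a permanent stop at counts of 75–150. The case for acting is that a mandatory safety rule contradicts a stated limit and that clarifying it is cheap. The conclusion assumes only that the rules mean what they say.

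**What to change.** Reconcile the Synopsis (Dose adjustment), Section 7.3.1 and Section 8.2.2 with Table 4. For a version 6.0–8.0 boy already reduced once, the platelet rule, the rule for resuming after a temporary stop and the one-reduction limit should lead to one stated action, the same at every site and whatever caused the first reduction. The sponsor, with the IDMC, should decide what that action is; this review does not propose one.

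The cost is a short protocol amendment or a clarification letter to sites, with no extra visits or patients.

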**For subjects randomized under protocol version 4.0:**

Study drug can be reduced by 1/3 of the starting dose at which the AE leading to temporary stop occurred, once platelets and/or white blood cell and/or hemoglobin are normalized and/or triglycerides return to levels below 300 mg/dL (3.42 mmol/L), or diarrhoea is mild. The subject may have more than the usual number of scheduled visits if needed, until the AE resolves, and then will continue the study as per scheduled visits.

If a subject was randomized with baseline triglycerides above 300 mg/dL (3.42 mmol/L) the Investigator can discuss how to manage the case with the medical monitor, however the final decision remains with the Investigator only or its authorized designee.

In addition, in case a subject will have a consistent (e.g., at least two consecutive evaluations) platelets count  $\leq 150 \times 10^9/L$  and not meeting the stopping criteria for platelets, the Investigator will have to reduce the dose by 1/3 vs the starting dose (see Section 8.2.2 for more details).

If a subject has a medical event not necessarily drug related that requires interruption of study drug dosing for >4 weeks, the Investigator can discuss the case with the medical monitor if the subject may resume study drug treatment, however the final decision remains with the Investigator only or its authorized designee.

Moreover, for subjects who have already reduced the dose of 1/3 an additional reduction of 20% is allowed for safety reasons following the instruction in section "*For subjects randomized under protocol version 6.0, or 7.0 or 8.0*".

Any decision relevant to the dose interruption and/or modification of the schedule of assessments can be discussed with the Medical Monitor, but the final decision remains with the Investigator only or its authorized designee.

## 8 TREATMENTS

### 8.1 Details of Study Treatments

The investigational study drug to be used in this study is givinostat (ITF2357) and a placebo. For the duration of the study, givinostat and placebo will be supplied by Italfarmaco S.p.A.

	Investigational Medicinal Drug	
	Test treatment	Comparator
Product name:	ITF2357/givinostat*	Placebo
Dosage form:	Oral suspension	Oral suspension
Unit dose strength:	Bottle containing 140 mL of givinostat 10 mg/mL	Bottle containing 140 mL of placebo
Route of Administration	Oral administration under fed conditions	Oral administration under fed conditions
Dosing instructions:	See Table 2	See Table 2
Physical description:	White to off-white or faintly pink, homogenous suspension when mixed	White to off-white or faintly pink, homogenous suspension when mixed
Device included in the packaging:	Two graduated dosing syringes for oral use: One 5 mL syringe and One 1 mL syringe	Two graduated dosing syringes for oral use: One 5 mL syringe and One 1 mL syringe

\*Givinostat is used to indicate the whole study drug name givinostat hydrochloride monohydrate. The dosages/concentrations of the study drug are expressed as givinostat hydrochloride monohydrate.

The investigational sites will be supplied initially with a congruous number of suspension bottles, in order to have sufficient supply of study drug to treat subjects who are enrolled in the study.

### 8.2 Dosage

#### 8.2.1 Rational for Dose Selection

The dose for this study has been selected based on: the dose ranging evaluation done in the mdx model; the results of the Phase 2 study in DMD paediatric subjects (DSC/11/2357/43), and the evaluation of PK and efficacy results obtained in other inflammatory diseases.

The PK/PD analysis done with the data collected during the non-clinical studies in mdx model, showed that a blood  $AUC_{0-24}$  of at least 300 ng\*h/mL was estimated to be needed to

exert the beneficial histological and functional effects in mouse and thus was considered the target exposure for the exploratory Phase 2 study in the DMD population (DSC/11/2357/43 study).

The study DSC/11/2357/43 was designed to first verify that doses of givinostat leading to an  $AUC_{0-24}$  of at least 300 ng\*h/mL in the majority of DMD subjects were tolerated and then to verify that such exposures would translate into a significant histological benefit. Results have confirmed that doses of 25/37.5 mg bid are tolerated, do result in an  $AUC_{0-24}$  of at least 300 ng\*h/mL in the majority of treated DMD subjects, and result in a significant histological benefit.

On the other hand, previous clinical experience in chronic inflammatory diseases in adult and paediatric populations (i.e., Crohn's Disease, Psoriasis, Systemic Onset Juvenile Idiopathic Arthritis and Polyarticular Course Juvenile Idiopathic Arthritis) have shown that givinostat was overall not efficacious in controlling symptoms and biological features of these diseases at exposures ( $AUC_{0-24}$ ) lower or comparable to those obtained in study DSC/11/2357/43.

Lack of efficacy of doses lower than those tested in study DSC/11/2357/43 were also suggested by the post-hoc analysis of study DSC/11/2357/43 results which showed that a 37.5 mg bid dose was associated with a larger increase in CSA of fibers compared to 25 mg bid.

Based on these considerations, the Sponsor believes that doses leading to daily exposures lower than those obtained in study DSC/11/2357/43 are very unlikely to be efficacious and therefore chose an initial study dose to ensure a mean  $AUC_{0-24}$  similar to that achieved with 37.5 mg/bid (i.e., approximately 1150 ng\*h/mL). As of 18th of June 2018, based on blinded safety haematologic data, the Sponsor has evaluated that, a vast majority of randomized subjects who had completed at least 8 weeks of treatment (approximately 50 to 60%) had to reduce the starting dose due to a decrease in platelet levels. It is, therefore, expected that a relevant amount of subjects that will be enrolled into the study will need to require the same dose adjustment. Therefore, a new starting dose corresponding to the reduced dose (i.e. 1/3 lower than the starting dose) of protocol version 4.0 (i.e. 13.3-46.7 mg/bid according to body weight) is proposed by the Sponsor in protocol version 6.0. This new starting dose ensures a mean  $AUC_{0-24}$  similar to that achieved with 25 mg/bid during the DSC/11/2357/43 study in

DMD patients (i.e., approximately 674 ng\*h/mL), which was safe and showed significant histological benefit.

As weight was shown to significantly affect givinostat clearance, and the study will enroll paediatric DMD subjects with a broad range of weight, the initial dose will be adjusted to the current body weight of the subject (see Table 2). A strict monitoring of platelets count has been planned, and it will be followed with dose adjustment instruction as described in the safety rules as described in Section 7.3.1 in order to avoid the risk of platelet reduction  $<75 \times 10^9/L$ .

### 8.2.2 Dosage Schedule

The following is a description of the dosage, treatment regimen, and route of administration. Givinostat oral suspension (10 mg/mL) and placebo oral suspension have to be administered orally as 2 oral doses daily while the subject is in a fed state. Before its use, the suspension must be shaken for at least 30 seconds by rotating the bottle by 180° and the homogeneity of the obtained suspension verified. The suspension will be administered by means of a graduated dosing syringe. The dosage to be administered is based on subject weight and the starting doses are described below:

